2.0 OBJECTIVES

2.1 Primary Objective

Pilot study of multichannel endoesophageal brachytherapy applicator to determine dose distribution and conformality of a 6 channel balloon repositioning applicator.

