3.2 Number of Subjects

Approximately 5 subjects will be enrolled in this trial.

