3.3 Replacement of Subjects

If subject does not receive the esophageal brachytherapy treatment, they will be excluded from the trial and another subject will be selected.

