3.4 Expected Duration of Treatment and Subject Participation

The initial treatment session will occur after the patient has been found to be eligible, the consent form has been completed, and the treatment plan has been created. The patient will undergo subsequent weekly treatments for 3 to 6 weeks after the initial treatment.

The subject will be expected to participate in the trial throughout its entirety. The participation period is 6 months of which the patient will be evaluated and seen at months 3 and 6.

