6.0 TREATMENT PLAN

6.1 Radiation Therapy

6.1.1 General Guidelines and Timing

Radiation therapy treatment planning

Patients will be planned using our standard 3D, CT-based, Oncentra treatment planning system. The target volume will be identified during endoscopy and an approximately 2 cm proximal and distal margin will be added to account for microscopic tumor extension (beyond the gross macroscopic disease) and to account for any spatial inaccuracy of the applicator device positioning. The dose will be prescribed to treat the target volume with modification if necessary to decrease doses to the normal surrounding tissues.

Intraoperative procedure

In the operating room, the patient's pulse, pulse oximetry, and blood pressure are obtained prior to the procedure and during the procedure. The patient is typically medicated with Demerol (100 mg IV) and Versed (4 mg IV) throughout the procedure and Benzocaine topically prior to the procedure as per standard anesthesia practices for esophageal brachytherapy patients. The endoscope is passed through the mouth under direct visualization and advanced distally, typically to the stomach or 2nd portion of the duodenum. The scope is then gradually withdrawn and the mucosa is examined. Of note, if a significant area of stenosis is identified, this is dilated to allow for a sufficient diameter for insertion of the brachytherapy applicator. Once the cancerous mucosa is visualized, radio-opaque markers (endoclips or metallic seeds) are placed with ~2 cm margins on the proximal and distal ends of the tumor. A guidewire is then passed to the stomach and the endoscope is removed. Over the guidewire, the brachytherapy applicator device is then placed under fluoroscopic guidance ensuring that the distal end travels past the most distal radio-opaque endoclip and typically into the stomach. The brachytherapy applicator is then stabilized and secured by inflating the anchor balloon and/or fixing to the mouth guard after removal of the guidewire.

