6.1.2 Equipment and Techniques to be used

After applicator placement, the patient is transported to the Department of Radiation Oncology for a CT simulation. Metal dummy seeds are placed into the channels. The treatment balloon is inflated to move the channels in close proximity to the esophageal tumor. The patient is placed in the supine position and undergoes a planning CT scan of the neck and thorax. The CT images are downloaded into the Oncentra treatment planning system and then tumor volume as well as normal critical structures are outlined by the treating radiation oncologist. During the treatment planning phase, the patient is transported to the nursing unit for observation. Following completion of treatment planning, the patient is transported to the HDR brachytherapy treatment room and maintained on the transport cart in the supine position. The exterior portions of the brachytherapy channels are connected to the remote afterloader HDR device. AnIridium-192 seed will enter the channels to deliver the planned course of brachytherapy. After treatment delivery, the brachytherapy channels are disconnected from the HDR afterloader device. After deflation of the anchor and treatment balloons and disconnection from the mouthpiece the multichannel applicator is removed gently from the patient. No devices will remain in the patient. The patient is subsequently transported to the nursing unit for vital sign monitoring for approximately one-half hour prior to discharge to home.

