6.1.4 Dose to Target and Organs at Risk Constraints

Typical dosimetry constraints, such as the dose delivered to 90% of the tumor volume (D90) and the volume of the tumor receiving the prescription dose (V100) will be reviewed to ensure that an acceptable treatment plan is designed. The use of our new applicator will improve the dose homogeneity as well as lower the dose to the nearby normal organs.

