14.0 STATISTICAL CONSIDERATIONS

This section outlines the statistical analysis strategy and procedures for the study. If, after the study has begun, changes made to primary and/or key secondary hypotheses, or the statistical methods related to those hypotheses, then the protocol will be amended (consistent with ICH Guideline E-9).

A variety of statistical methods will be employed to analyze the trials's data. Data will be periodically analyzed using descriptive statistics and correlative measures for significance when comparing demographic and dosimetric data. Typical dosimetry constraints, such as the dose delivered to 90% of the tumor volume (D90) and the volume of the tumor receiving the prescription dose (V100) will be reviewed to ensure that an acceptable treatment plan is designed. The use of our new applicator will improve the dose homogeneity as well as lower the dose to the nearby normal organs.

As this application is specifically for a new device to deliver the same doses of radiation therapy previous administered using single or multi-tube approaches, we will analyze data on patient outcome and dosimetry data in comparison with our historical controls. Specifically, we will use endoscopic follow-up images and correlate the visual changes with the radiation therapy doses delivered to the tumor, esophageal wall, and nearby organs at risk. One of the limitations of esophageal brachytherapy is the lack of the treating physician's ability to modulate the dose when using a single tube device.

The currently utilized and innovative approach used in our department is a 3-tube technique. Use of the 3-tube technique improves the dose homogeneity and reduces the doses to heart, lungs, bronchus, trachea, and vertebral bodies. In addition to nonoperable patients with esophageal cancer undergoing definitive therapy, patients with recurrent or metastatic disease may symptomatically benefit from HDR brachytherapy. In fact, a randomized controlled trial

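### Section 3.3 excludes untreated subjects whatever the reason, so an undeliverable 6-channel plan or a failed placement can drop out of a pilot meant to describe that device

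*Combined protocol and SAP*

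**What the plan says.** All references are to the combined protocol and SAP.

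- **Primary objective (2.1):** "to determine dose distribution and conformality of a 6 channel balloon repositioning applicator".
- **Sample size (3.2):** "Approximately 5 subjects will be enrolled in this trial". No precision target or power calculation supports the number.
- **Replacement (3.3):** "If subject does not receive the esophageal brachytherapy treatment, they will be excluded from the trial and another subject will be selected".
- **Order of events (3.0, 3.4, 6.1.2):** the applicator is placed, a planning CT is taken, structures are outlined and the plan is made. Then: "Following completion of treatment planning, the patient is transported to the HDR brachytherapy treatment room". Section 3.4 likewise puts the first session after the plan exists.
- **Plan review (6.1.4, repeated in 3.0 and 14.0):** D90 and V100 "will be reviewed to ensure that an acceptable treatment plan is designed". No threshold is given.
- **Plan adjustment (6.1.1):** "The dose will be prescribed to treat the target volume with modification if necessary to decrease doses to the normal surrounding tissues".
- **Comparison (14.0):** "we will analyze data on patient outcome and dosimetry data in comparison with our historical controls".
- **Record of exclusions (5.0):** a reason is required for subjects who consent but are not enrolled. Nothing equivalent covers a subject who is enrolled, has a plan made and is then excluded under 3.3.

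No section defines an evaluable set, retains an excluded subject's plan, or asks for the number of attempted placements.

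**The concern.** Replacing untreated subjects is a sensible way to reach about five treated patients for the toxicity objective. Excluding them is a separate step, and the primary objective does not need it. Dose distribution and conformality are read from the plan, so they exist whether or not the dose is given.

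An exclusion rule that depends on delivery can therefore discard primary data already in hand. If non-delivery is connected with a poor plan, the discarded data are the unfavourable ones. Two results are exposed:

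1. **The dosimetry description.** It could become a description of plans good enough to deliver, with a mean that is too favourable and a spread that is too small.
2. **The feasibility count.** How often the device can be placed and yields a deliverable plan is basic information from a pilot of a new applicator. Section 1.3 describes prior testing only of an earlier prototype, in a porcine model. Under 3.3 the numerator and denominator of that count are the same subjects.

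**Working it through.** **Stated figure.** The only number in the plan that bears on this is the sample size of about five. It has no derivation, so there is nothing to reproduce. The check concerns who is in the analysis set.

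**Step 1: which subjects can be lost.**

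| Situation | Plan exists? | Treated? | Effect of 3.3 |
|---|---|---|---|
| Applicator cannot be placed | No | No | Lost from the feasibility count; no dosimetry lost |
| No acceptable plan before the first session, even after modification | Yes | No (inferred) | Plan and failure both lost |
| Poor plan at a later session | Yes | Already treated | 3.3 does not apply |
| First plan poor, modified, then delivered | Yes | Yes | Nothing lost; redesign within a subject is not selection of subjects |

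Only the second row can distort the dosimetry. The first and second both distort the count.

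**Step 2: the count.** With five treated and k dropped for these reasons, the success proportion is 5/(5+k). Exact (Clopper-Pearson) 95% intervals are:

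| k | True result | 95% CI | Result under 3.3 |
|---|---|---|---|
| 0 | 5/5 = 100% | 48–100% | 5/5 |
| 1 | 5/6 = 83% | 36–99.6% | 5/5 |
| 2 | 5/7 = 71% | 29–96% | 5/5 |
| 3 | 5/8 = 63% | 24–91% | 5/5 |

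**Step 3: how likely a loss is.** Let q be the probability that a subject is dropped for one of these reasons. The documents give no value, so q is an assumption. The chance of at least one drop before five are treated is 1 − (1 − q)^5, and the expected number dropped is 5q/(1 − q).

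| q (assumed) | P(at least one drop) | Expected drops |
|---|---|---|
| 5% | 1 − 0.95^5 = 23% | 0.26 |
| 10% | 1 − 0.90^5 = 41% | 0.56 |
| 20% | 1 − 0.80^5 = 67% | 1.25 |

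**Step 4: the largest shift in the dosimetry.** Assume a normally distributed metric on which higher is better, and that each dropped plan is the worst on that metric.

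- 1 of 6 dropped: the expected minimum of six standard normals is −1.267. All six sum to zero in expectation, so the other five average 1.267/5 = +0.25 SD.
- 2 of 7 dropped: the expected two lowest of seven are −1.352 and −0.757, so the other five average (1.352 + 0.757)/5 = +0.42 SD.
- By simulation, the expected sample SD of five values falls from 0.94 (no selection) to 0.78 and 0.70 respectively.

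**Step 5: a weaker link.** If the reason for dropping correlates only 0.3 to 0.5 with the reported metric, the 1-of-6 shift is 0.3 × 0.253 = 0.08 SD to 0.5 × 0.253 = 0.13 SD, with expected sample SD 0.93 to 0.90. If the two are unrelated, the shift is zero.

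**The case against.** **The review of D90 and V100 is not stated to be a gate.** A reader might infer that treatment goes ahead only once those values pass. The documents do not say so. They describe the review as serving plan design, set no threshold, and name modification as the response to unwanted dose. That an unacceptable plan leads to no treatment is an inference from the purpose of the review and the order of events. This objection stands, and it limits the point to what 3.3 *can* do.

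**The historical comparison is not shown to be biased.** A reader might also infer that 3.3 tilts the comparison with the 3-tube technique towards the new device. Section 1.4 describes the 3-tube series as patients who were treated, so it too is conditioned on delivery. Delivered against delivered is like-for-like. Setting all 6-channel plans against delivered 3-tube plans would create an imbalance against the new device. This stands, and it shapes the fix.

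**D90 and V100 are not named as the primary endpoint.** The objective is dose distribution and conformality; these two are called typical constraints. This stands, and it is why Step 4 is an upper case.

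**The route is narrow and the trial is small and descriptive.** Only failures before the first delivered session count, and no test or success threshold depends on the result. A switch to another applicator is not addressed either; such a subject might not meet the wording of 3.3. All this lowers the likely frequency. It does not answer the rule itself, which has no exception, and with about five subjects one removal is visible.

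**Numbers entered may be recoverable.** Section 5.0 registers every consented subject in OnCore. That preserves a head count, but not the plan or the reason for non-delivery after enrolment.

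**Conclusion.** The point holds as a weakness in the exclusion rule. Followed as written, 3.3 can remove an undeliverable 6-channel plan from the primary dosimetry and a failed attempt from the record, and no other section restores either.

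The effect on the count is certain whenever such a failure occurs: 5/6 or 5/7 would appear as 5/5. The effect on dosimetry is of unknown size. It is zero if nobody is dropped for this reason. In expectation it is at most about +0.25 SD (1 of 6) or +0.42 SD (2 of 7), under normality and with the dropped plans always worst on the reported metric; with a weaker link it is smaller. The dosimetric effect also rests on the inference that a subject with no acceptable plan goes untreated.

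The correction should be made because it is nearly free, not because a large bias has been demonstrated.

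**What to change.** 1. **Reword 3.3**, for example: *A subject who receives no brachytherapy may be replaced so that about five treated subjects are available, but remains in the trial for reporting. The final 6-channel plan for each subject and session, delivered or not, is included in the primary dosimetry description; superseded drafts are not.* Naming the final plan per subject and session fixes the unit of analysis and keeps drafts replaced during optimisation out of the table.
2. **Report the count by subject:** the number with a delivered 6-channel plan out of all in whom applicator placement was attempted, with the reason for each failure.
3. **Keep the 3-tube comparison on delivered plans** in both groups, and say so in section 14.0.

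None of this alters a treatment decision. Any undelivered plan already exists, so the cost is a short edit to 3.3, a line in 14.0 and one extra table row. The downside is that the headline dosimetry may look slightly less favourable.

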3.4 Expected Duration of Treatment and Subject Participation

The initial treatment session will occur after the patient has been found to be eligible, the consent form has been completed, and the treatment plan has been created. The patient will undergo subsequent weekly treatments for 3 to 6 weeks after the initial treatment.

The subject will be expected to participate in the trial throughout its entirety. The participation period is 6 months of which the patient will be evaluated and seen at months 3 and 6.

4.0 SUBJECT SELECTION

Each of the criteria in the sections that follow must be met in order for a subject to be considered eligible for this study. Use the eligibility criteria to confirm a subject's eligibility.

4.1 Inclusion Criteria

Subjects must meet all of the following inclusion criteria to be eligible for enrollment:

1. Biopsy-proved esophageal adenocarcinoma or squamous cell carcinoma
2. Disease that can be encompassed in the radiotherapy treatment field
3. Age \geq 18 years: Because no dosing or adverse event data are currently available on the use of esophageal brachytherapy in subjects \leq 18 years of age, children are excluded from this study.”

4. Women of childbearing potential must practice adequate contraception
5. Subjects must have the ability to understand and the willingness to sign a written informed consent document.

4.2 Exclusion Criteria

The presence of any of the following will exclude a subject from study enrollment.

1. Concurrent chemotherapy at the time of brachytherapy treatments
2. Tracheal or bronchial involvement
3. Cervical esophagus location
4. Stenosis that cannot be bypassed or dilated to allow for applicator placement
5. Not willing or unable to provide informed consent
6. History of esophageal fistula

4.3 Inclusion of Women and Minorities

Men and women at or over the age of 18, and members of all races and ethnic groups are eligible for this trial.

5.0 REGISTRATION

All subjects who have been consented are to be registered in the OnCore™ Database. For those subjects who are consented, but not enrolled, the reason for exclusion must be recorded.

All subjects will be registered through Cleveland Clinic Florida's Maroone Cancer Center and will be provided a study number by contacting [name] at [contact] or [contact].

Eligible subjects will be enrolled into the trial and treated as per standard of care.

6.0 TREATMENT PLAN

6.1 Radiation Therapy

6.1.1 General Guidelines and Timing

Radiation therapy treatment planning

Patients will be planned using our standard 3D, CT-based, Oncentra treatment planning system. The target volume will be identified during endoscopy and an approximately 2 cm proximal and distal margin will be added to account for microscopic tumor extension (beyond the gross macroscopic disease) and to account for any spatial inaccuracy of the applicator device positioning. The dose will be prescribed to treat the target volume with modification if necessary to decrease doses to the normal surrounding tissues.

Intraoperative procedure

In the operating room, the patient's pulse, pulse oximetry, and blood pressure are obtained prior to the procedure and during the procedure. The patient is typically medicated with Demerol (100 mg IV) and Versed (4 mg IV) throughout the procedure and Benzocaine topically prior to the procedure as per standard anesthesia practices for esophageal brachytherapy patients. The endoscope is passed through the mouth under direct visualization and advanced distally, typically to the stomach or 2nd portion of the duodenum. The scope is then gradually withdrawn and the mucosa is examined. Of note, if a significant area of stenosis is identified, this is dilated to allow for a sufficient diameter for insertion of the brachytherapy applicator. Once the cancerous mucosa is visualized, radio-opaque markers (endoclips or metallic seeds) are placed with ~2 cm margins on the proximal and distal ends of the tumor. A guidewire is then passed to the stomach and the endoscope is removed. Over the guidewire, the brachytherapy applicator device is then placed under fluoroscopic guidance ensuring that the distal end travels past the most distal radio-opaque endoclip and typically into the stomach. The brachytherapy applicator is then stabilized and secured by inflating the anchor balloon and/or fixing to the mouth guard after removal of the guidewire.

6.1.2 Equipment and Techniques to be used

After applicator placement, the patient is transported to the Department of Radiation Oncology for a CT simulation. Metal dummy seeds are placed into the channels. The treatment balloon is inflated to move the channels in close proximity to the esophageal tumor. The patient is placed in the supine position and undergoes a planning CT scan of the neck and thorax. The CT images are downloaded into the Oncentra treatment planning system and then tumor volume as well as normal critical structures are outlined by the treating radiation oncologist. During the treatment planning phase, the patient is transported to the nursing unit for observation. Following completion of treatment planning, the patient is transported to the HDR brachytherapy treatment room and maintained on the transport cart in the supine position. The exterior portions of the brachytherapy channels are connected to the remote afterloader HDR device. AnIridium-192 seed will enter the channels to deliver the planned course of brachytherapy. After treatment delivery, the brachytherapy channels are disconnected from the HDR afterloader device. After deflation of the anchor and treatment balloons and disconnection from the mouthpiece the multichannel applicator is removed gently from the patient. No devices will remain in the patient. The patient is subsequently transported to the nursing unit for vital sign monitoring for approximately one-half hour prior to discharge to home.

6.1.3 Target Volumes

Patients will be treated using standard radiation therapy dosing guidelines, typically in 2-6 sessions separated by weekly intervals. In addition to identifying the treatment volume (CTV, PTV), the organs at risk will be identified.

6.1.4 Dose to Target and Organs at Risk Constraints

Typical dosimetry constraints, such as the dose delivered to 90% of the tumor volume (D90) and the volume of the tumor receiving the prescription dose (V100) will be reviewed to ensure that an acceptable treatment plan is designed. The use of our new applicator will improve the dose homogeneity as well as lower the dose to the nearby normal organs.

6.7 Criteria for Removal from Study

In the absence of treatment delays due to adverse events, treatment may continue for up to 6 cycles or until one of the following criteria applies:

- Disease progression,
- Intercurrent illness that prevents further administration of treatment,
- The investigator considers it, for safety reasons, to be in the best interest of the subject.
- General or specific changes in the subject's condition render the subject unacceptable for further treatment in the judgment of the investigator,
- Subject decision to withdraw from treatment (partial consent) or from the study (full consent),
- Pregnancy during the course of the study for a child-bearing participant
- Death
- Sponsor reserves the right to temporarily suspend or prematurely discontinue this study. The date and reason for discontinuation must be documented. Every effort should be made to complete the appropriate assessments.

6.8 Duration of Follow Up

Subjects will be followed for 6 months after the initial procedure or until death, whichever occurs first.

The clinical course of each event will be followed until resolution, stabilization, or until it has been determined that the study treatment or participation is not the cause.

Serious adverse events that are still ongoing at the end of the study period will necessitate follow-up to determine the final outcome. Any serious adverse event that occurs after the study period and is considered to be possibly related to the study treatment or study participation will be recorded and reported immediately.

